### **MRI: Calculated Contractile Muscle Volume**

Individual calculated contractile muscle volume data will be listed. Descriptive statistics will be provided by treatment group and scheduled time for raw data and changes from baseline (absolute and percent change). Absolute and percent changes from baseline will be provided for each side (left and right) as well as the average of the left and right sides. This will be done for the double-blind, placebo-controlled component as well as for the open-label component.

For the double-blind component, the plot of mean ( $\pm$  SEM) for the average of left and right side percent change in calculated contractile muscle volume from baseline (average of left and right sides) by scheduled day and treatment group for each muscle group (BB and TA) during the double-blind period as well as during the open-label extension period.

For the double-blind component, an ANCOVA model will be fitted in order to assess the effect of ACE-083 on the Day 190 average percent change from baseline in calculated contractile muscle volume for the left and right sides. Covariates to be included in the model are: MUSCLE, TREATMENT, BASELINE, MRC-MMT GRADE CATEGORY, MUSCLE\*TREATMENT, and BASELINE\*MUSCLE where:

- MUSCLE represents the muscle treated (BB or TA)
- TREATMENT represents the treatment group (ACE-083 or placebo)
- BASELINE represents the baseline calculated contractile muscle volume (average of left and right sides)
- MRC-MMT GRADE CATEGORY represents the randomization stratification factor (3 to 4- or 4- to 4+)
- MUSCLE\*TREATMENT represents the muscle-by-treatment interaction
- BASELINE\*MUSCLE represents the baseline-by-muscle interaction

The effect of ACE-083 on the Day 190 average percent change in calculated contractile muscle volume from baseline of the injected TA or BB versus placebo will be estimated using the ANCOVA model described above and tested using a 0.1 significance level (2-sided) separately for TA and BB. The least square mean estimate along with the corresponding 90% confidence interval will be provided separately for TA and BB. In addition, the 95% confidence interval will also be provided as well as a bar chart of the least squares mean estimates ( $\pm$  SEM) for each of the treatment groups separately for TA and BB.

A mixed model repeated measures (MMRM) analysis will be performed to assess the sensitivity to the ANCOVA analysis described above. An unstructured covariance structure will be used to model the within-patient covariance across visits. Other covariance structures will be considered if the unstructured covariance fails. The covariates to be included consist of all of the covariates described above for the ANCOVA with the addition of the following additional covariates: VISIT where VISIT represents the scheduled visit day post first dose of MRI assessment (D43, D106, D190), MUSCLE\*VISIT, TREATMENT\*VISIT, and MUSCLE\*TREATMENT\*VISIT.

For both the ANCOVA and MMRM analyses, multiple imputations will be performed for missing data. Twenty imputations will be performed. Imputations will be performed separately for BB and TA patients. The seed to be used is specified in [Section 6](#). The assumption of the missing data mechanism will be missing at random (MAR) unless the data suggest otherwise. The missing data pattern (monotone or arbitrary) will also be evaluated and the regression method for imputing missing data will be utilized for each scheduled timepoint with missing data. Covariates to be included when imputing missing data include: MRC-MMT GRADE CATEGORY, TREATMENT, BASELINE, and CCMV percent change data at scheduled timepoints prior to the timepoint at which CCMV percent change is being imputed.

The table below illustrates the covariates that should be used for imputing missing data:

Data to be Imputed	Covariates to use in Multiple Imputation Regression Model
Baseline CCMV	MRC-MMT GRADE CATEGORY, TREATMENT, MUSCLE*TREATMENT
Day 43 Percent change in CCMV from baseline	MRC-MMT GRADE CATEGORY, TREATMENT, BASELINE
Day 106 Percent change in CCMV from baseline	MRC-MMT GRADE CATEGORY, TREATMENT, BASELINE, Day 43 CCMV percent change
Day 190 Percent change in CCMV from baseline	MRC-MMT GRADE CATEGORY, TREATMENT, BASELINE, Day 43 CCMV percent change, Day 106 CCMV percent change

Analysis findings will be presented for Day 190 percent change data where missing data is not imputed (observed data) as well as for Day 190 percent change data where multiple imputations are performed for missing data to assess the impact of the missing data on the observed study data. The analyses where multiple imputations are performed are considered to be primary.

For BB patients, the above analyses will be repeated using the patient's "preferred" side used for the PUL test for patients.

The Per Protocol Set will be used for the primary analysis. The analyses described above will also be repeated for the Full Analysis Set.

Additional analyses may be performed as appropriate.

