## 1. INTRODUCTION

This statistical analysis plan (SAP) provides a comprehensive and detailed description of strategy and statistical techniques to be used to analyze data for study protocol A083-02. The purpose of the SAP is to ensure the credibility of the study findings by pre-specifying the statistical approaches to the analysis of study data prior to database lock.

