##### **Primary Efficacy Analysis (Double-Blind Phase)**

###### **MRI: Total Muscle Volume**

Individual total muscle volume data will be listed. Descriptive statistics will be provided by treatment group and scheduled time for raw data and changes from baseline (absolute and percent change). Absolute and percent changes from baseline will be provided for each side (left and right) as well as the average of the absolute change and average of the percent change for the left and right sides. This will be done for the double-blind, placebo-controlled component as well as for the open-label component.

For the double-blind component, the plot of mean ( $\pm$  SEM) for the average of left and right side percent change in total muscle volume from baseline by scheduled day and treatment group for each muscle group (BB and TA) during the double-blind period as well as during the open-label extension period will be provided.

For the double-blind component, an ANCOVA model will be fitted in order to assess the effect of ACE-083 on the Day 190 average percent change from baseline in total muscle volume for the left and right sides. Covariates to be included in the model are MUSCLE, TREATMENT, BASELINE, MRC-MMT GRADE CATEGORY, MUSCLE\*TREATMENT, and BASELINE\*MUSCLE where:

- MUSCLE represents the muscle treated (BB or TA)
- TREATMENT represents the treatment group (ACE-083 or placebo)
- BASELINE represents the baseline total muscle volume (average of left and right sides)
- MRC-MMT GRADE CATEGORY represents the randomization stratification factor (3 to 4- or 4- to 4+)
- MUSCLE\*TREATMENT represents the muscle-by-treatment interaction
- BASELINE\*MUSCLE represents the baseline-by-muscle interaction

The effect of ACE-083 on the percent change in TMV from baseline of the injected TA or BB at Day 190 versus placebo will be estimated using the ANCOVA model described above and tested using a 0.1 significance level (2-sided) separately for TA and BB. The least squares mean estimate along with the corresponding 90% confidence interval will be provided separately for TA and BB. In addition, the 95% confidence interval will also be provided as well as a bar chart

of the least squares mean estimates ( $\pm$  SEM) for each of the treatment groups separately for TA and BB.

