A mixed model repeated measures (MMRM) analysis will be performed to assess the sensitivity to the ANCOVA analysis described above. An unstructured covariance structure will be used to model the within-patient covariance across visits. Other covariance structures will be considered if the unstructured covariance fails. The covariates to be included consist of all of the covariates described above for the ANCOVA with the addition of the following additional covariates: VISIT where VISIT represents the scheduled visit day post first dose of MRI assessment (D43, D106, D190), MUSCLE\*VISIT, TREATMENT\*VISIT, and MUSCLE\*TREATMENT\*VISIT.

For both the ANCOVA and MMRM analyses, multiple imputations will be performed for missing data. Twenty imputations will be performed. The seed to be used is specified in Section 5. The assumption of the missing data mechanism will be missing at random (MAR) unless the data suggest otherwise. The missing data pattern (monotone or arbitrary) will also be evaluated and the regression method for imputing missing data will be utilized for each scheduled timepoint with missing data. Covariates to be included when imputing missing data include: MRC-MMT GRADE CATEGORY, TREATMENT, BASELINE, MUSCLE\*TREATMENT, and TMV percent change data at scheduled timepoints prior to the timepoint at which TMV percent change is being imputed.

The table below illustrates the covariates that should be used for imputing missing data:

Data to be Imputed	Covariates to use in Multiple Imputation Regression Model
Baseline TMV	MRC-MMT GRADE CATEGORY, MUSCLE, TREATMENT, MUSCLE*TREATMENT
Day 43 Percent change in TMV from baseline	MRC-MMT GRADE CATEGORY, MUSCLE, TREATMENT, MUSCLE*TREATMENT, BASELINE
Day 106 Percent change in TMV from baseline	MRC-MMT GRADE CATEGORY, MUSCLE, TREATMENT, MUSCLE*TREATMENT, BASELINE, Day 43 TMV percent change
Day 190 Percent change in TMV from baseline	MRC-MMT GRADE CATEGORY, MUSCLE, TREATMENT, MUSCLE*TREATMENT, BASELINE, Day 43 TMV percent change, Day 106 TMV percent change

Analysis findings will be presented for Day 190 percent change data where missing data is not imputed (observed data) as well as for Day 190 percent change data where multiple imputations are performed for missing data to assess the impact of the missing data on the observed study data. The analyses where multiple imputations are performed are considered to be primary.

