A mixed model repeated measures (MMRM) analysis will be performed to assess the sensitivity to the ANCOVA analysis described above. An unstructured covariance structure will be used to model the within-patient covariance across visits. Other covariance structures will be considered if the unstructured covariance fails. The covariates to be included consist of all of the covariates described above for the ANCOVA with the addition of the following additional covariates: VISIT where VISIT represents the scheduled visit day post first dose of MRI assessment and TREATMENT\*VISIT.

For both the ANCOVA and MMRM analyses, multiple imputations will be performed for missing data. Twenty imputations will be performed. The seed to be used is specified in [Section 6](#). The assumption of the missing data mechanism will be missing at random (MAR) unless the data suggest otherwise. The missing data pattern (monotone or arbitrary) will also be evaluated and the regression method for imputing missing data will be utilized for each scheduled timepoint with missing data. Covariates to be included when imputing missing data include: MRC-MMT GRADE CATEGORY, TREATMENT, BASELINE, and MVIC percent change data at scheduled timepoints prior to the timepoint at which MVIC percent change is being imputed.

The table below illustrates the covariates that should be used for imputing missing data for selected timepoints:

Data to be Imputed	Covariates to use in Multiple Imputation Regression Model
Baseline MVIC	MRC-MMT GRADE CATEGORY, TREATMENT
Day 22 Percent change in MVIC from baseline	MRC-MMT GRADE CATEGORY, TREATMENT, BASELINE
Day 43 Percent change in MVIC from baseline	MRC-MMT GRADE CATEGORY, MUSCLE, TREATMENT, MUSCLE*TREATMENT, BASELINE, Day 22 MVIC percent change
Day 190 Percent change in MVIC from baseline	MRC-MMT GRADE CATEGORY, MUSCLE, TREATMENT, MUSCLE*TREATMENT, BASELINE, Days 22, 43, 64, 85, 106, and 148 MVIC percent change from baseline

Note: The above is to be applied for elbow flexion MVIC (BB treated patients) and ankle dorsiflexion (TA treated patients).

Analysis findings will be presented for Day 190 percent change data where missing data is not imputed (observed data) as well as for Day 190 percent change data where multiple imputations are performed for missing data to assess the impact of the missing data on the observed study data. The analyses where multiple imputations are performed are considered to be primary.

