## 6. PROGRAMMING SPECIFICATIONS

### Seed to Use for Multiple Imputations of Missing Data

The seed to be used for multiple imputations of MRI data is 1111.

The seed to be used for multiple imputations of FSHD-HI data is 2222.

The seed to be used for multiple imputations of TA functional data is 3333.

The seed to be used for multiple imputations of PUL data is 4444.

The seed to be used for multiple imputations of elbow flexion MVIC data is 5555.

The seed to be used for multiple imputations of ankle dorsiflexion MVIC data is 6666.

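### Twenty imputations leave avoidable Monte Carlo noise in the primary Day 190 p-values; it matters only for results close to 0.10, and raising the number costs almost nothing

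*SAP*

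**What the plan says.** The TMV text in SAP 4.7.2.2 reads "Twenty imputations will be performed. The seed to be used is specified in Section 5". The cross-reference is wrong: Section 5 lists modifications from the protocol, and the seeds are in Section 6, for example "The seed to be used for multiple imputations of MRI data is 1111".

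The same number is set for calculated contractile muscle volume ("Twenty imputations will be performed. Imputations will be performed separately for BB and TA patients"), fat fraction, calculated intramuscular fat, MVIC, 10-meter walk/run, 6-minute walk distance, 4-stair climb, mid-level PUL and FSHD-HI. It is set again for the open-label comparisons in 4.7.2.3. For each of these endpoints the SAP states: "The analyses where multiple imputations are performed are considered to be primary".

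TMV is "tested using a 0.1 significance level (2-sided) separately for TA and BB". The other MRI, strength and motor-function endpoints are tested at the same level. FSHD-HI receives 90% and 95% intervals without a stated test.

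The SAP gives no reason for choosing twenty, no check of Monte Carlo error, and no rule for a result close to 0.10.

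**The concern.** Twenty imputations are ample for the efficiency of the point estimate. With a fraction of missing information (FMI) of 0.02 to 0.17, the relative efficiency 1/(1 + FMI/20) is 0.999 to 0.992. They are less adequate for the p-value and the confidence limits, because the pooled estimate and the between-imputation variance both still vary from one set of twenty to the next. Fixing the seed makes this error repeatable but does not remove it.

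What is at stake is the reading of a borderline result. A p of 0.095 under seed 1111 might have been 0.11 under 1112 on the same patients, and nothing in the planned output would show it.

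**Working it through.** **The plan's own figure.** With 12 per arm, a difference of 10, SD 9 and two-sided alpha 0.10, the noncentrality is 10/(9·√(2/12)) = 2.72 on 22 df, with critical value 1.717. Exact t-test power is 83.9%, in line with the stated 83%.

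**Inputs from the documents.** There are 20 imputations, a two-sided 0.10 level, 14 randomized per arm per muscle and dropout of up to 15% (SAP 4.1.1). The TMV ANCOVA pools both muscles with six terms plus an intercept, so residual df are 56 − 7 = 49.

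**Assumed, because the documents are silent.** Day 190 is missing in 1 or 2 of 14 per arm (7% or 14%), with between-visit correlation about 0.7 to 0.85. A wider simulated range of 0.3 to 0.9 gave FMI of 0.02 to 0.17, and that range is used below.

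**Step 1: noise in p.** The Monte Carlo SD of the pooled t statistic is about √(FMI/m). Near p = 0.10 the SD of p is therefore about 2·f(1.677)·√(FMI/m), where f is the t density on 49 df and f(1.677) = 0.0984. For FMI 0.10 and m = 20 this is 2 × 0.0984 × √0.005 = 0.0139. The band below holds the converged p-values within 1.96 Monte Carlo SDs of the threshold.

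| FMI | SD of p, m = 20 | m = 200 | m = 500 | Band, m = 20 | Band, m = 500 |
|---|---|---|---|---|---|
| 0.02 | 0.0062 | 0.0020 | 0.0012 | 0.088–0.113 | 0.098–0.102 |
| 0.05 | 0.0098 | 0.0031 | 0.0020 | 0.082–0.121 | 0.096–0.104 |
| 0.10 | 0.0139 | 0.0044 | 0.0028 | 0.076–0.130 | 0.095–0.106 |
| 0.17 | 0.0181 | 0.0057 | 0.0036 | 0.069–0.141 | 0.093–0.107 |

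**Step 2: converged p in 0.08 to 0.12.** Averaged over this band, the formula puts 12% (FMI 0.02) to 30% (FMI 0.17) of twenty-imputation runs on the other side of 0.10. At m = 500 the figures are 2.5% to 7%.

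**Step 3: over all possible results.** The chance that the verdict at m differs from the converged verdict is as follows.

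| Truth | P(0.08 < p < 0.12) | m = 20 | m = 200 | m = 500 |
|---|---|---|---|---|
| No effect | 4.0% | 0.5–1.5% | 0.2–0.5% | 0.1–0.3% |
| Planned effect, 13 per arm | 4.3% | 0.5–1.5% | 0.2–0.5% | 0.1–0.3% |
| About 50% power | 8.1% | 1.0–2.9% | 0.3–0.9% | 0.2–0.6% |

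**Step 4: simulation.** The formula ignores noise in the between-imputation variance, so the procedure was also simulated (Bayesian regression imputation, Rubin's rules, small-sample df). At correlation 0.7 to 0.85, the SD of p for a converged p in 0.08 to 0.12 was 0.005 to 0.020, and 7 to 31% of runs crossed 0.10. Over correlations of 0.3 to 0.9, the SD for a converged p in 0.09 to 0.11 was 0.006 to 0.022.

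The walking endpoints are somewhat noisier. Their Day 190 imputation model has seven prior visits, stratum, treatment, height, baseline and an intercept. That is 12 coefficients from about 24 to 26 observed patients. With 2 missing per arm and correlation 0.7, this raised FMI from 0.09 to 0.11.

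**The case against.** A reader might infer that the arbitrary seed decides whether these endpoints are significant. The documents do not support that.

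- **Selection.** The SAP states its purpose as "pre-specifying the statistical approaches to the analysis of study data prior to database lock", and Section 6 lists all six seeds. A seed cannot be picked after seeing the result, so there is no route to bias or to type I error inflation. This stands in full.
- **Frequency.** The 10 to 30% figure applies only when the converged p is between 0.08 and 0.12, which happens in about 4% of tests under no effect or the planned effect. Even there, most runs agree with the converged verdict. Simulation at about 50% power, with per-muscle models, can give overall rates of 1.5 to 4.4%. That is where near-threshold results are most common, and it is not the power planned for TMV. Power for most secondary endpoints is not stated, so intermediate power cannot be excluded for them.
- **Missingness.** The 15% is a ceiling. The primary set is the Per Protocol Set, which drops patients who discontinue before Day 43, and replaced patients are not imputed (SAP 4.1.5 and 4.2). A one-sided MRI or strength value stands in for the average, and a Day 190 assessment up to 7 days after dosing is kept. These rules push FMI towards the lower rows of the tables, where noise is smaller but not zero.
- **Context.** Observed-data results, which need no seed, are reported alongside, as are 90% and 95% intervals. This helps interpretation. However, the observed-data result is not the primary one and does not show how much of the imputed p is Monte Carlo error.

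**Conclusion.** The point holds as a minor one. Near 0.10, twenty imputations leave an SD of roughly 0.005 to 0.02 in the primary imputed p-values, and roughly 10 to 30% of runs would cross the threshold when the converged p is 0.08 to 0.12. Averaged over all results, the verdict changes in about 0.5 to 1.5% of tests under no effect or the planned effect, and in up to about 3% at intermediate power. All these sizes rest on the assumed missingness and correlation. Outside the bands in the table, twenty is adequate for the FMI expected here. The validity of the analysis is not in question; the noise is simply avoidable.

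**What to change.** Before database lock, replace twenty with a larger number throughout SAP 4.7.2.2 and 4.7.2.3, starting with the TMV paragraph. At least 200 is reasonable: the SD of p falls by √(200/20), about 3.2-fold. At 500 it falls by √(500/20) = 5-fold, to about 0.001 to 0.004. Keep the pre-specified seeds. Report the Monte Carlo error of the estimate and of the p-value for each primary imputed analysis. The subgroup analyses in 4.7.2.4 refer back to 4.7.2.2 and inherit the change. In the same edit, correct the TMV cross-reference for the seed from Section 5 to Section 6.

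The cost is one number in the SAP, a line of output per analysis and a little computing time. No patients, visits or data are added.

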### **MRI: Fat Fraction**

For fat fraction data, the absolute change from baseline (by side and average of left and right sides) of the injected TA or BB will be summarized for each scheduled time. Such summaries will also be done for raw data and percent change from baseline.

For the double-blind component, an ANCOVA model will be fitted in order to assess the effect of ACE-083 on the Day 190 absolute change in fat fraction from baseline data (average of left and right sides). Covariates to be included in the model are MUSCLE, TREATMENT, MRC-MMT GRADE CATEGORY, BASELINE, BASELINE\*MUSCLE and MUSCLE\*TREATMENT where BASELINE represents the baseline fat fraction (average of left

and right sides) and each of the other covariates are defined similarly as what was done for the primary efficacy analysis.

The effect of ACE-083 on the Day 190 absolute change of fat fraction from baseline (average of left and right sides) of the injected TA or BB versus placebo will be estimated using the ANCOVA model described above and tested using a 0.1 significance level (2-sided) separately for TA and BB. The least-square mean estimate along with the corresponding 90% confidence interval will be provided. In addition, the 95% confidence interval will also be provided separately for TA and BB.

A mixed model repeated measures (MMRM) analysis will be performed to assess the sensitivity to the ANCOVA analysis described above. An unstructured covariance structure will be used to model the within-patient covariance across visits. Other covariance structures will be considered if the unstructured covariance fails. The covariates to be included consist of all of the covariates described above for the ANCOVA with the addition of the following additional covariates: VISIT where VISIT represents the scheduled visit day post first dose of MRI assessment (D43, D106, D190), MUSCLE\*VISIT, TREATMENT\*VISIT, and MUSCLE\*TREATMENT\*VISIT.

For both the ANCOVA and MMRM analyses, multiple imputations will be performed for missing data. Twenty imputations will be performed. The seed to be used is specified in [Section 6](#). The assumption of the missing data mechanism will be missing at random (MAR) unless the data suggest otherwise. The missing data pattern (monotone or arbitrary) will also be evaluated and the regression method for imputing missing data will be utilized for each scheduled timepoint with missing data. Covariates to be included when imputing missing data include: MRC-MMT GRADE CATEGORY, TREATMENT, BASELINE, and FF absolute change data at scheduled timepoints prior to the timepoint at which FF absolute change is being imputed.

The table below illustrates the covariates that should be used for imputing missing data:

Data to be Imputed	Covariates to use in Multiple Imputation Regression Model
Baseline FF	MRC-MMT GRADE CATEGORY, TREATMENT,
Day 43 Absolute change in FF from baseline	MRC-MMT GRADE CATEGORY, TREATMENT, BASELINE
Day 106 Absolute change in FF from baseline	MRC-MMT GRADE CATEGORY, TREATMENT, BASELINE, Day 43 FF absolute change
Day 190 Absolute change in FF from baseline	MRC-MMT GRADE CATEGORY, TREATMENT, BASELINE, Day 43 FF absolute change, Day 106 FF absolute change

Analysis findings will be presented for Day 190 percent change data where missing data is not imputed (observed data) as well as for Day 190 percent change data where multiple imputations are performed for missing data to assess the impact of the missing data on the observed study data. The analyses where multiple imputations are performed are considered to be primary.

For BB patients, the above analyses will be repeated using the patient's "preferred" side used for the PUL test for patients.

The Per Protocol Set will be used for the primary analysis. The analyses described above will also be repeated for the Full Analysis Set.

Additional analyses may be performed as appropriate.

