For both the ANCOVA and MMRM analyses, multiple imputations will be performed for missing data. Imputations will be performed separately for the BB and TA patients. Twenty imputations will be performed. The seed to be used is specified in [Section 6](#). The assumption of the missing data mechanism will be missing at random (MAR) unless the data suggest otherwise. The missing data pattern (monotone or arbitrary) will also be evaluated and the regression method for imputing missing data will be utilized for each scheduled timepoint with missing data. Covariates to be included when imputing missing data include: MRC-MMT GRADE CATEGORY, TREATMENT, BASELINE, and CIMF (volume or mass) percent change data at scheduled timepoints prior to the timepoint at which CIMF (volume or mass) percent change is being imputed.

The table below illustrates the covariates that should be used for imputing missing data:

Data to be Imputed	Covariates to use in Multiple Imputation Regression Model
Baseline CIMF	MRC-MMT GRADE CATEGORY, TREATMENT
Day 43 Percent change in CIMF from baseline	MRC-MMT GRADE CATEGORY, TREATMENT, BASELINE
Day 106 Percent change in CIMF from baseline	MRC-MMT GRADE CATEGORY, TREATMENT, BASELINE, Day 43 CIMF percent change
Day 190 Percent change in CIMF from baseline	MRC-MMT GRADE CATEGORY, TREATMENT, BASELINE, Day 43 CIMF percent change, Day 106 CIMF percent change

Note: The above is to be applied for volume (CIMFV) as well as mass (CIMFM).

Analysis findings will be presented for Day 190 percent change data where missing data is not imputed (observed data) as well as for Day 190 percent change data where multiple imputations are performed for missing data to assess the impact of the missing data on the observed study data. The analyses where multiple imputations are performed are considered to be primary.

The Per Protocol Set will be used for the primary analysis. The analyses described above will also be repeated for the Full Analysis Set.

Additional analyses may be performed as appropriate.

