#### **Open-Label Extension vs. Double-Blind Placebo-Controlled Phase**

#### **Selected MRI, and FSHD-HI Total Score and FSHD-HI Activity Limitation Subscale Score**

For total muscle volume, calculated contractile muscle volume, fat fraction, FSHD-HI total score, and FSHD-HI activity limitation subscale score, descriptive statistics will be provided for the Placebo □ ACE-083 treatment sequence for the difference in percent (or absolute) change observed between Day 190 and pre-first treatment baseline (1st 6 months) and the percent (or absolute) change observed between Day 358 and the open-label treatment baseline (2nd 6 months).

In addition, the effect of ACE-083 administered during the open-label extension compared to the treatment administered in the double-blind placebo-controlled phase will be examined for those receiving ACE-083 during the double-blind phase and separately for those receiving placebo during the double-blind phase by comparing the percent (or absolute) change observed between Day 190 and pre-first treatment baseline (1st 6 months) and Day 358 versus the open-label treatment baseline (2nd 6 months) using an ANCOVA model for each individual data parameter.

Covariates to be included into the model are MUSCLE, SEQUENCE, MRC-MMT GRADE CATEGORY, BASELINE, and MUSCLE\*SEQUENCE where:

- MUSCLE refers to the muscle treated (i.e. BB or TA)
- SEQUENCE refers to the treatment sequence from double-blind to open-label (ACE-083 □ ACE-083 or Placebo □ ACE-083)

- MRC-MMT GRADE CATEGORY refers to the randomization stratification factor from the double-blind phase
- BASELINE refers to baseline from the double-blind phase
- MUSCLE\*SEQUENCE refers to the muscle-by-sequence interaction

Least squares estimates of the SEQUENCE\*MUSCLE effect and the corresponding 90% confidence interval will be provided and will be tested using a 0.1 significance level (2-sided). In addition, the least squares estimates for each sequence along with the corresponding 90% confidence interval will be provided separately for each muscle and will be tested using a 0.1 significance level (2-sided).

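### The fat-fraction imputation takes no account of muscle, although the analysis it feeds is by muscle: a small, avoidable bias when data are missing

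*SAP*

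**What the plan says.** SAP 4.7.2.2, MRI: Fat Fraction, fits one ANCOVA over both muscles with `MUSCLE`, `TREATMENT`, MRC-MMT category, `BASELINE`, `BASELINE*MUSCLE` and `MUSCLE*TREATMENT`. The effect is "tested using a 0.1 significance level (2-sided) separately for TA and BB". On missing data, "For both the ANCOVA and MMRM analyses, multiple imputations will be performed for missing data", and "The analyses where multiple imputations are performed are considered to be primary".

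The imputation rule is "Covariates to be included when imputing missing data include: MRC-MMT GRADE CATEGORY, TREATMENT, BASELINE, and FF absolute change data at scheduled timepoints" before the one being filled in. The four table rows (baseline, Days 43, 106 and 190) follow it. None contains a muscle term, and the section does not say that TA and BB are imputed apart. The conventions in SAP 4.1.5, the subgroup section (4.7.2.4) and the programming specifications (Section 6) do not supply this either.

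The other double-blind endpoints that are modelled jointly over both muscles and imputed do allow for muscle:

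- Total muscle volume (TMV), by covariates; its Day 106 row is "MRC-MMT GRADE CATEGORY, MUSCLE, TREATMENT, MUSCLE*TREATMENT, BASELINE, Day 43 TMV percent change".
- Calculated contractile muscle volume (CCMV): "Imputations will be performed separately for BB and TA patients".
- Calculated intramuscular fat (CIMF): "Imputations will be performed separately for the BB and TA patients".
- FSHD-HI, by the same sentence as CIMF.

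FF itself is handled by muscle in the open-label comparison (SAP 4.7.2.3). That analysis covers "For total muscle volume, calculated contractile muscle volume, fat fraction, FSHD-HI total score, and FSHD-HI activity limitation subscale score", and its imputation includes `MUSCLE` and `MUSCLE*SEQUENCE`.

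**The concern.** An imputation model should hold at least the terms whose effects are then estimated and tested. Here it lacks the muscle main effect, the interaction that separates the two tests, and the baseline-by-muscle slope. Given earlier visits, a missing FF value is drawn with one intercept and one conditional treatment effect for both muscles. The completed data then go into a model that reports TA and BB separately, and that result is primary. The imputed MMRM uses the same draws, so it is no independent check. The FF subgroup analyses reuse the same approach.

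It looks like an omission. The FF covariate list matches the CIMF list apart from the variable name; only the sentence on separate imputation is absent. SAP 4.7.1.1 derives CCMV and CIMF volume from TMV and FF, so two variables computed from FF are imputed by muscle while FF is not. SAP Section 5 gives no reason for the difference.

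**Working it through.** **The plan's own figure.** None exists for FF. The nearest is 83% power for TMV (12 per arm, difference 10, SD 9, two-sided 0.10). The noncentrality is 10 / (9 × √(2/12)) = 2.72 on 22 df, and the exact t calculation gives 83.9%, which agrees.

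**Inputs from the documents.** 14 per arm per muscle and dropout up to 15% (SAP 4.1.1); 20 imputations and the ANCOVA terms (Fat Fraction section). All FF effects, SDs, visit profiles and dropout patterns below are assumptions.

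**Mechanism.** Suppose there were no earlier visits to lean on, and missing proportions mA (active) and mP (placebo) were the same in both muscles. Write δk for the true effect in muscle k, and μAk and μPk for the arm means, with a bar for the average over muscles. The expected estimate is

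δk − mA(μAk − μ̄A) + mP(μPk − μ̄P).

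- *Balanced dropout m.* This reduces to δk − m(δk − δ̄). For -5/-1 at 15%: TA -5 + 0.15 × 2 = -4.70 and BB -1 − 0.15 × 2 = -1.30, a pull of 0.30. At 5% the pull is 0.10.
- *Equal effects, muscles differing by c in mean change.* The bias is (mA − mP) × c/2 in size, with opposite signs in the two muscles. With c = 4, mA = 25% and mP = 5%, that is 0.20 × 2 = 0.40.

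Earlier FF changes recover part of the muscle difference, so simulated values are mostly smaller.

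**Simulation, main case.** TA -5 / BB -1, 14 per arm per muscle, patient and residual SD 2, 40/70/100% of the effect at Days 43/106/190, 15% missing after Day 43. Sequential-regression imputation, 20 imputations, Rubin's rules; 2,500 trials for the ANCOVA and 600 for the MMRM.

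| Analysis | As written (TA / BB) | With `MUSCLE`, `MUSCLE*TREATMENT` | Split by muscle |
|---|---|---|---|
| Imputed ANCOVA | -4.74 / -1.24 | -4.98 / -1.01 | -4.98 / -1.00 |
| Imputed MMRM | -4.80 / -1.24 | -5.05 / -1.00 | not run |

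The observed-data MMRM gives -5.05 / -1.01. The ANCOVA pull is about 0.24 per muscle, so the gap of 4 shrinks by 0.48 (12%). Against a standard error of 1.24 that is 0.24 / 1.24 = 0.19. Repeat simulations gave -4.74 / -1.26 and -4.68 / -1.21 as written.

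**Other balanced-dropout cases (shrinkage of the gap).**

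- 5% missing: 4%, which is 0.04 × 4 / 2 = 0.08 per muscle.
- Effects -4/-2: 13%. Other SDs: 10–14%.
- Flat profile: 7% (missing after Day 43) or 4% (Day 190 only).
- Waning profile (150/125/100%): 3% or 1%. With residual SD 1 and only Day 190 missing, the gap widens by 2%.
- Equal effects (-3/-3): -2.99 / -2.99, no bias.

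A different set of assumptions (TA 0, BB -5, SD 3, visit correlation 0.6, 15% missing, 14 per arm) gives a gap of -4.43 as written and -5.01 with muscle terms.

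**Unbalanced dropout.**

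- True -3/-3, c = 4, dropout 5% placebo and 25% active: -3.31 / -2.66 as written, -3.01 / -2.96 with muscle terms. With c = 2: -3.19 / -2.85 against -3.02 / -3.00.
- True gap -5, muscle main effect -5, 30% dropout in placebo only, 300 per arm to isolate bias: the gap widens to -5.88. With the dropout in active only, it shrinks to -3.07.

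**Accuracy at trial size, balanced dropout (TA / BB).**

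| Measure | As written | With muscle terms |
|---|---|---|
| RMSE, main case | 1.16 / 1.17 | 1.18 / 1.20 |
| RMSE, residual SD 1 | 0.94 / 0.88 | 0.91 / 0.85 |
| 90% CI coverage, main case | 0.93 / 0.92 | 0.91 / 0.90 |
| BB rejection, BB null and TA -5 (nominal 0.10) | 0.087 | 0.107 |

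**The case against.** The best defence is that with 14 per arm, sharing information between muscles trades a little bias for less variance. The main-case RMSE is slightly lower as written, coverage is at or above nominal, and type I error is not inflated. This stands, though at residual SD 1 the RMSE is slightly worse as written.

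Second, 15% is near the ceiling. The primary FF analysis uses the Per Protocol Set, which SAP 4.2 defines to exclude discontinuations before Day 43, and SAP 4.1.5 does not impute replaced early dropouts. Missingness in the primary analysis is therefore probably below 15%, and the 5% result deserves equal weight. The Full Analysis Set repeat has more exposure, and single scans can be missed.

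Third, the documents give no ground for expecting FF effects as different as -5 and -1. Protocol 7.1 expects similar tissue exposure in the two muscles, and SAP 4.1.1 carries the TMV assumptions over to BB. That also stands; the sizes above are illustrations.

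A reader might go further and infer that every missing value is drawn with a single treatment effect for both muscles, or that FF inference is invalid. Neither follows. The Day 106 and Day 190 rows condition on earlier FF changes, which already carry some muscle-specific response; only what remains is shared. Observed-data results are also reported.

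**Conclusion.** The mismatch is plain in the text and is a minor defect. It biases the per-muscle FF estimates under identifiable conditions. With similar dropout in both arms and effects that differ by muscle, the estimates are usually pulled together: about 0.24 FF points each at 15% missing and 0.08 at 5% in the assumed building-up case, and less if the effect is flat or waning. At most this is about a fifth of a standard error in the main case.

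A reader might infer that the rule is harmless whenever the two effects are equal, or that it always understates the difference. Neither is general. If the muscles differ in mean change and dropout differs by arm, equal effects can appear unequal, or the gap can widen. Bias is absent if nothing is missing, or if effects are equal and dropout is balanced across arms.

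FF is a secondary endpoint. The findings on coverage, type I error and RMSE at trial size come from balanced dropout only. Nothing here shows that a trial conclusion would change.

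**What to change.** In SAP 4.7.2.2, MRI: Fat Fraction, add the sentence used for CCMV: "Imputations will be performed separately for BB and TA patients". This aligns FF with CCMV and CIMF and also covers the baseline-by-muscle slope.

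Alternatively, add `MUSCLE` and `MUSCLE*TREATMENT` to the covariate sentence and all four rows, and `BASELINE*MUSCLE` to the sentence and the three post-baseline rows. Copying the TMV table alone would leave `BASELINE*MUSCLE` out.

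The cost, if effects are truly equal (-3/-3) with 15% missing, is some per-muscle power (TA / BB): 0.81 / 0.81 as written, 0.79 / 0.80 with `MUSCLE` and `MUSCLE*TREATMENT` added (about 2 points), and 0.77 / 0.78 if split (about 3 to 5 points, allowing for rounding). The cost of also adding `BASELINE*MUSCLE` was not computed. The change should be made before unblinding.
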